**8.5. Description of study procedures for maternal subjects**

This section lists procedures to be performed / data to be recorded during the study and presents additional details where relevant. For the study procedures schedule, refer to [Table 5](#).

**8.5.1. Eligibility Review and Confirmation**

- Obtain Informed consent as described in [Sections 6.2.1](#) and [7.1](#).
- Check all applicable inclusion and exclusion criteria as described in [Sections 6.2](#) and [6.3](#) before enrollment and record results.
- Assign / record subject study number (pregnant woman)
- Assign subject study number (infant) for eligible pregnant women who complete Visit 1.
- For eligible pregnant women who complete visit 1 (are enrolled): ensure that site study physicians (both obstetrician(s) and pediatrician(s)) are informed. In particular, the study pediatrician and/or staff should be notified as soon as possible after a pregnant woman's enrolment to ensure the study pediatrician is informed of the approximate date of delivery and potential enrolment of the neonate.

**CONFIDENTIAL**207636 (EPI-RSV-008 BOD)  
Protocol Amendment 4 Final**8.5.2. History for maternal subjects**

- Distribute the Maternal Subject Card (Section [9.3](#)).
- Distribute the Maternal Diary Card to the subject (Section [8.5.4](#)).
- Record demographic data, which may include (but are not limited to) information such as geographic ancestry (race), month and year of birth, and ethnicity.
- Record information about lifestyle characteristics (exposures), which may include (but are not limited to) data on highest level of education, factors such as smoking status/exposures, household environment, and other factors that could place subjects at risk of study outcomes.
- Record information about whether (during the current pregnancy) the subject has travelled to / is living in countries / regions with Zika virus transmission.
- Where authorized by the local Ethics Committee, inquire whether mother would have agreed to take part in the study if an investigational vaccine were given and record the answer.
- Record outcome of Level 2 ultrasound (fetal morphology assessment). Please see [GLOSSARY OF TERMS](#) for description. If Level 2 ultrasound results are not available at screening, then the ultrasound can be performed as a study procedure under certain conditions. Refer to the SPM for further details.
- ONLY record outcome(s) of any subsequent ultrasound(s) if clinically significant.
- Record the subject's pre-pregnancy weight (i.e., weight during the months before the subject became pregnant) in the subject's eCRF. This information can be obtained either via medical record review or subject interview.
- Confirm that the subject's pre-pregnancy BMI is within the range specified in Section [6.2.1](#). This information can be obtained from the medical record, or, if unavailable, may be calculated based on the subject's height and reported pre-pregnancy weight.
- Obtain the subject's medical and obstetric history by interview and/or review of her medical records. Record any pre-existing conditions or signs and/or symptoms present before participation in the study
  - For past pregnancies, record:
    - Number of past pregnancies and their outcome(s),
    - Presence of caesarian section scars (if any).
  - For the current pregnancy, record:
    - Gestational age, along with GAIA level of certainty, using priorities defined in [APPENDIX C](#).
    - Expected date of delivery (EDD) and method of estimation
    - Number of prenatal visits attended up to the date of the study Screening visit,

**CONFIDENTIAL**207636 (EPI-RSV-008 BOD)  
Protocol Amendment 4 Final

- Approximate date of first prenatal visit,
- Results of any clinically significant, abnormal pregnancy screening laboratory tests,
- Results of any procedures intended to screen for congenital anomalies.

### **8.5.3. Examinations of maternal subjects**

#### **Record results of General and Obstetric examinations.**

- Record height at screening. Height measurements should be performed preferentially by local healthcare providers, in which case the information will be collected and recorded in the mother's eCRF. If not done by the local healthcare provider as per local practice, the investigator/study staff should perform the measurement.
- Unless the study visit is performed concurrently with a routine care visit at which the below data are collected, the investigator/study staff should perform General and Obstetric examinations as follows:
  - Screening and Visits 1 - 4 should include assessment of weight, fetal heart tones, fetal movement, and fundal height;
  - Screening, Visits 1 to 4, and Visit 6 should include assessment of temperature, systolic/diastolic blood pressure, heart rate and respiratory rate after at least 10 minutes of rest) and blood oxygen saturation by pulse oximetry.
  - If the Screening Visit and Visit 1 occur on the same day, only one General and Obstetric examination will be performed.

### **8.5.4. Maternal Diary Card**

A maternal diary card will be provided to each subject at visit 1, then collected and replenished throughout the study as needed. It will document any prescription medications, folate and/or iron (independently or included in a multivitamin) taken, any vaccinations received during pregnancy and after delivery, and any additional visits the subject may make to a healthcare provider not affiliated with the study.

The diary card will be reviewed with the subject during study visits. If review indicates that the subject visited a healthcare provider not affiliated with the study, study staff should (if permitted by local regulation) contact that healthcare provider to obtain the medical record(s) for the visit.

Refer to the SPM for additional details.

### **8.5.5. Biological Specimens / Laboratory Data for maternal subjects**

- The Investigator/site staff will arrange for collection of maternal blood and cord blood samples at delivery.
- The Investigator/site staff will perform urine dipstick tests using supplies provided by GSK.

**CONFIDENTIAL**207636 (EPI-RSV-008 BOD)  
Protocol Amendment 4 Final

- If HIV test results are not available at time of screening, the HIV test can be performed as a study procedure under certain conditions. Refer to the SPM for further details. If results are positive, the subject will be referred per local standard of care.
- It is preferred that local healthcare providers perform hematology and biochemistry tests per local practice; the investigator/site staff will then collect and record the results. The investigator/site staff will only perform hematology/biochemistry tests if not done by the local healthcare provider within 2 weeks before a study visit.
- If performed by local healthcare provider and results are available, the investigator/site staff will also:
  - Record oral glucose challenge / oral glucose tolerance test results
  - Record any positive urine bacterial culture results
  - Record abnormal and clinically significant laboratory test results
  - Record results of Group B Streptococcus screening test(s).

**8.5.6. Labor / Delivery**

Record information related to labor and delivery, including:

- Any medications administered during labor and delivery as per standard of care if not considered routine
- Date and time of rupture of membranes
- Date and time of delivery
- Type of delivery
- Other delivery related information relevant to the health and safety of the mother and fetus

**8.5.7. Medications, vaccinations, and supplements administered to maternal subjects as per standard of care**

Record medications / vaccinations / folate and iron supplements beginning the month before the estimated date of conception and while on study. Folic acid and/or iron supplements should be reported when taken independently and/or when included in a multivitamin mineral supplement.

**8.5.8. Outcomes and Events of Interest in maternal subjects (Amended 29-MAY-2020)**

- Record delivery and pregnancy outcomes. Of note, fetal death/stillbirth has multiple subcategories. For example, fetal death/stillbirth with no congenital anomalies is an outcome with two subcategories that include: 1) antepartum stillbirth; 2) intrapartum stillbirth. For each outcome, the investigator should select the applicable sub-category.

**CONFIDENTIAL**207636 (EPI-RSV-008 BOD)  
Protocol Amendment 4 Final

- If there is no live birth, all study visits and procedures related to the maternal subject should still be followed up to study end.
- Record pregnancy related events of interest.
  - The investigator will review all medical records pertaining to prenatal care based on GAIA definitions ([APPENDIX D](#)) when applicable.
  - Maternal events of interest (including, but not limited to, those described in Section [11.1.1](#)) occurring up to Visit 6 (Post-delivery Day 42) should be recorded in the eCRF along with additional details pertinent to the diagnosis, GAIA assessment and level of diagnostic certainty ([APPENDIX D](#)), when applicable. Of note, some events of interest fall under a single category but have multiple subcategories. For example, hypertensive disorders of pregnancy is an event with three subcategories that include: 1) gestational hypertension; 2) pre-eclampsia; and 3) pre-eclampsia with severe features (including eclampsia). For each event, the investigator should identify the event and select the applicable sub-category.
  - Information about maternal hospitalizations, clinically significant events, and diagnoses that could impact the pregnancy will be recorded.
  - Any events of interest in mother or fetus will be referred to and managed by the routine health services as locally appropriate.
- Record all hospitalizations and/or clinically significant events, ***including COVID-19 cases***.
- Record all study participation related SAEs as specified in Section [9](#).

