### **3. OBJECTIVES**

#### **3.1. Primary objectives**

*In healthy pregnant women with uncomplicated pregnancies:*

- To determine the frequencies of pregnancy outcomes.
- To determine the frequencies of pregnancy related events of interest from enrollment (Visit 1) through 42 days after delivery (Visit 6). (Although pregnancy related events of interest occur within the first 42 days after delivery they may only be detected later, and are to be reported throughout the study.)

*In all neonates live-born to women enrolled in the study:*

- To determine the frequencies of neonatal events of interest.

Neonatal events of interest occur within the first 28 days after birth, but may only be detected later and are to be reported throughout the study.

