**Table 1 Sampling schedule for maternal subjects**

Sample	Parameter(s) evaluated	Visit				
		1	2	3	4	Delivery
Maternal Blood	Hematology/ biochemistry 		x		x 	
	Antibody titer (RSV-A)					≤ 72 hours after delivery 
Cord Blood	Antibody titer (RSV-A)					x
Urine	Protein, glucose, RBC, WBC 	x	x	x	x	

 To be performed preferentially by local healthcare providers, as per local practice. To be performed by the investigator/study staff ONLY if not done by the local healthcare provider within 2 weeks before the study visit.

 The investigator/site staff will perform a urine dipstick test using supplies provided by GSK.

 Hemoglobin only

 If results are abnormal, subjects will be referred per local standard of care.

 This sample may be collected from start of labor (e.g. when the mother arrives at the hospital to deliver and an intravenous line is inserted) through 72 hours after delivery.

- Sampling schedule for **neonates/infants**: Surveillance for RSV LRTI will be conducted in infants through the 12 month study period. During this 1-year post-birth surveillance period, for each RTI with suspicion of difficulty in breathing, or wheezing, or with parental concern, a nasal swab will be collected at a visit to assess potential RSV associated RTIs/LRTIs.
- Primary Completion Date (PCD): 42 days post-delivery/birth (i.e. Visit 6 for maternal subjects and Visit 2-NB for infant subjects) or last visit of Epoch 002.
- End of Study (EoS): Last testing results released of samples collected up to Visit 4-NB (assays related to primary and secondary endpoints).
- Duration of the study: Approximately 4.5 to 6 months for maternal subjects; approximately 1 year for infant subjects.
  - Epoch 001: Screening
  - Epoch 002: Primary starting at Visit 1 and ending 42 days post-delivery/birth (Visit 6 for maternal subjects and Visit 2-NB for infant subjects).\*
  - Epoch 003: Follow-up of infants starting 43 days post-delivery/birth and ending at Visit 4-NB (1 year post-birth).

\*Any safety and disease surveillance data collected after Visit 2-NB will be collected in Epoch 003.

**CONFIDENTIAL**207636 (EPI-RSV-008 BOD)  
Protocol Amendment 4 Final**Table 2 Study groups and epochs foreseen in the study**

Study Groups	Number of subjects enrolled	Age (Min/Max)	Epochs		
			Epoch 001	Epoch 002	Epoch 003
Maternal subjects	Up to ~ 2300	18 years - 45 years	x	x	

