**Table 7 Intervals between study visits/contacts/observations\* (Amended 29-MAY-2020)**

Interval	Optimal interval	Allowed interval**
Screening → Visit 1	1 days	0 - 28 days
Visit 1 → Visit 2**	28 days	21 -35 days
Visit 1 → Visit 3**	56 days	49 - 63 days
Visit 1 → Visit 4**	84 days	77 - 91 days
Maternal blood sample collection "at" Visit 5 (delivery)	0 days	0 (Start of labor) - 3 days (i.e., 72 hours post-delivery)
Visit 5 → Visit 6	42 days	35 - 49 days
Birth → Visit 1-NB	0 days	0 - 21 days
Birth → Visit 2-NB	42 days	35 - 49 days
Birth → Visit 3-NB	180 days	166 -194 days
Birth → Visit 4-NB	365 days	351 - 379 days

\*If other visits and medical evaluations are performed (outside of study visits/procedures), data should be collected in the electronic case report forms (eCRFs) (see [Section 8.5.7](#)).

\*\*If a subject returns for the visit outside the allowed time interval, he/she may still be considered for analysis.

Investigators should make at least 3 documented attempts (through telephone call(s) or any other convenient procedure) to contact (as relevant) the pregnant woman/mother or the child's parents/ LAR(s) (or their designates) if they do not return for scheduled visits or follow-up. Additional details can be found in the SPM.

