4	
Report of stillbirth but fetus is not available for physical examination after birth (no objective assessment can be made).
 
Maternal information insufficient to assess gestational age.

Reference: DaSilva FT, Gonik B, McMillan M, et al. Stillbirth: Case definition and guidelines for data collection, analysis, and presentation of maternal immunization safety data. Vaccine. 2016; 34(49):6057-6068.

**CONFIDENTIAL**207636 (EPI-RSV-008 BOD)  
Protocol Amendment 4 Final**Table 21      Maternal Death**

The death of a woman while pregnant or within 42 days of termination of pregnancy, irrespective of the duration and site of the pregnancy, from any cause related to or aggravated by the pregnancy or its management but not from accidental or incidental causes. (As ICD-10 terminology).

In the context of immunization: “Death of a woman during pregnancy, childbirth and the puerperium that is closely related temporally to an immunization event of the mother which is likely the single or contributory cause

Levels of Diagnostic Certainty (Highest level (1) to lowest level of certainty)	
Level	Description
1	
Diagnosis of pregnancy established by any of the following documented criteria:
 
 
a. Ultrasound examination
 
b. Fetal heart tones
 
c. Positive serum or urine human chorionic gonadotropin pregnancy test
 
d. Delivery of a neonate or other products of conception (abortus, stillborn)
 
 
AND
 
Death of the mother while pregnant or within 42 days of termination of pregnancy, irrespective of the duration and site of the pregnancy AND
 
Documentation of Cause of death as:
 
 
a. Direct: abortive outcome, hypertensive disorder, obstetric hemorrhage, pregnancy related infection, other obstetric complications, unanticipated complications
 
b. Indirect: non obstetric complications
 
c. Death during pregnancy, childbirth and the puerperium: other or coincidental
 

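### The 42-day maternal event window has no scheduled ascertainment for up to its last 7 days when Visit 6, the mother's concluding visit, falls before day 42.

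*Protocol*

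**What the plan says.** The primary objective in section 3.1 reads "To determine the frequencies of pregnancy related events of interest from enrollment (Visit 1) through 42 days after delivery (Visit 6", so the 42-day limit and the visit are written as the same thing. Section 11.1.1.2 heads the endpoint by visits (Visit 1 to Visit 6), and section 8.5.8 asks for events "occurring up to Visit 6 (Post-delivery Day 42) should be recorded in the eCRF along with additional details pertinent to the diagnosis". The glossary defines the events by the 42-day limit alone. In Appendix D, Table 21 counts "Death of the mother while pregnant or within 42 days of termination of pregnancy", and Table 24 puts the same 42-day limit on postpartum hemorrhage.

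The Table 7 entry for the visit is "Visit 5 → Visit 6 42 days 35 - 49 days": optimal day 42, allowed days 35 to 49. A footnote adds: "If a subject returns for the visit outside the allowed time interval, he/she may still be considered for analysis".

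Table 5 places the mother's study conclusion and the investigator's eCRF sign-off at Visit 6. Section 4 ends the maternal epoch there, and Table 2 gives mothers no Epoch 003. On late detection, section 3.1 says that events "may only be detected later, and are to be reported throughout the study"; section 11.1.1.2 repeats this.

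**The concern.** A fixed 42-day endpoint cannot be fully observed by a concluding visit that may take place a week earlier. A woman seen on day 35 has completed the study under section 10.1. She then enters the analysis as one woman in a percentage (section 11.6), not as person-time, so nothing in the estimate shows that her window was cut short. A death, hemorrhage or sepsis on day 38 would reach the data only if someone happened to learn of it.

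The study is meant to supply background rates against which safety data from future maternal vaccine trials will be read, and section 11.2 plans on about 180 to 270 evaluable women per country. For the rarest events, a single missed case can be the difference between none and one.

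**Working it through.** **Inputs**
- End of the endpoint window: day 42 after delivery (section 3.1, glossary, Appendix D Tables 21 and 24).
- Allowed Visit 6 dates: day 35 to day 49, optimal day 42 (Table 7).
- Last scheduled maternal assessment: Visit 6 (Table 5, Table 2).

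**Size of the gap.** For a Visit 6 on day v, days without scheduled ascertainment = max(0, 42 − v).
- v = 35: 42 − 35 = 7 days (days 36 to 42).
- v = 41: 42 − 41 = 1 day.
- v ≥ 42: 0 days.

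As a share of the postpartum part of the window, the maximum is 7/42 = 16.7%. As a share of all maternal observation it is smaller. Assume delivery at 40 0/7 weeks (day 280; my assumption, not the protocol's):
- Visit 1 at 24 0/7 weeks (day 168): 280 − 168 + 42 = 154 days; 7/154 = 4.5%.
- Visit 1 at 27 6/7 weeks (day 195): 280 − 195 + 42 = 127 days; 7/127 = 5.5%.

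Seven days is the maximum only for visits inside the allowed interval, because Table 7 lets visits outside it be analysed too.

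**Is there a later route into the data?**
- Maternal diary card (Table 5): handed out at Visits 1 to 5, collected at Visit 6, not reissued.
- Infant schedule (Table 6): no maternal-event item at any visit or contact.
- Active surveillance contacts (section 8.6.5.3): their stated purpose is the infant's respiratory symptoms and parental concern about them.
- Pregnancy without a live birth (section 8.5.8): maternal procedures continue to study end, which for the mother is Visit 6. There are no infant contacts.

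**Comparison with the neonatal endpoint.** That window closes at day 28, and the earliest allowed Visit 2-NB is day 35, which is 35 − 28 = 7 days after closure. Table 6 also repeats the recording of neonatal events at every scheduled visit to 12 months. The neonatal schedule therefore covers its window and provides for late detection. The maternal schedule can end 7 days before its window does.

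**The case against.** Several points on the other side stand.

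- A reader might infer that maternal events are recorded only up to Visit 6. The documents do not support that. Sections 3.1 and 11.1.1.2 require later-detected events to be reported throughout the study. The additional-evaluations column of Table 5 takes pregnancy-related events and hospitalizations, and its footnote 5 allows collection after a scheduled visit. These routes are real but passive: they let an event be entered once known, and nobody is scheduled to ask.
- A reader might also infer that the mother's eCRF closes at Visit 6. Table 5 asks only for sign-off before analysis, and section 11.11 analyses cleaned data after all subjects in all countries have finished Epoch 002. Closure is not stated.
- It is tempting to add that a day-49 visit brings a week of extra events into the count, so that two compliant women differ by 14 days. The glossary and the 42-day definitions largely exclude onsets on days 43 to 49, and section 11.6 leaves the tabulation windows to the SAP. That half is mainly a matter of wording.
- Day 42 is the optimal date, and many listed events, such as gestational diabetes or dysfunctional labor, cannot begin after delivery. For live births, contact with the parents continues, so a maternal death could well surface.

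What remains is that the SAP can drop late onsets but cannot supply days 36 to 42 if no one collected them.

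**Conclusion.** The concern holds as an ascertainment gap with a wording inconsistency behind it. For a woman whose in-interval Visit 6 falls on days 35 to 41, between 1 and 7 days of the primary window have no scheduled ascertainment, at most 16.7% of its postpartum part. Late reporting is required but not organised, and women without a live-born infant have no later contact at all.

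The effect on any event frequency cannot be computed: the protocol gives neither the distribution of Visit 6 dates nor the timing of events in days 36 to 42. A reader might go on to conclude that rates will not be comparable between countries or with a later trial. That would need visit timing to differ by site and events to occur in those days, and the documents show neither. The point is worth correcting because it touches a primary endpoint, no analysis can repair it, and the remedy is cheap.

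**What to change.** - Keep the 35 to 49 day interval. Table 5 footnote 4 pairs Visit 6 with Visit 2-NB, which has the same interval; moving Visit 6 to, say, days 42 to 56 would leave only days 42 to 49 in common and strain that pairing.
- For any woman seen before day 42, defer her study conclusion. Ask one scripted maternal-event question, covering vital status and date of onset, at the first infant surveillance contact on or after day 42, or by telephone if there is no live infant. The onset date matters because contacts outside the RSV season are about monthly, so the answer may come some weeks after day 42.
- In sections 8.5.8 and 11.1.1.2, replace the Visit 6 bound by onset on or before day 42 after delivery, in line with the glossary.

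The cost is a wording change, one extra question at a contact that already takes place, and a brief call for the few women without infant contacts.

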#### **8.5.9. Additional Antenatal / medical evaluations external to study visits / procedures**

For any additional antenatal / medical evaluations at which a pregnancy related event of interest is identified, record information that supports the diagnosis of the event, if available.

